7.4.4 Off Neoadjuvant Chemotherapy

The reason for off neoadjuvant chemotherapy will be taken from Off Neoadjuvant Chemotherapy Section of CRF Chemotherapy Report.

The following information will be summarized (**Table 22**):

- Number of patients off neoadjuvant chemotherapy
- Reason off neoadjuvant chemotherapy

7.5 **Surgical Treatments**

Tumour excision are performed within 2-5 weeks (for patients on FOLFOX) or 3-6 weeks (for patients on CAPOX) after first dose of last cycle of chemotherapy after a pre-excision visit performed within 2 weeks after the first dose of the last cycle (cycle 6) of FOLFOX therapy or within 3 weeks after the first dose of the last cycle (cycle 4) of CAPOX. Information from pre-excision visit and on the surgical treatment will be taken respectively from the CRF Pre-Excision Report and CRF Surgery Report.

7.5.1 Pre-excision Characteristics and MRI results

- Weight: median, minimum, maximum values (**Table 23**)
- BSA: median, minimum, maximum values (**Table 23**)
- ECOG Performance Status: 0, 1 (**Table 23**)
- cT-stage: T0, Tis, T1, T2, T3a, T3b, T3c, T3d, T4a, T4b, Tx (**Table 23**)
- Node positive disease: Yes, No (**Table 23**)
- Clear circumferential radial margin (CRM): Yes, No (**Table 23**)
- Progressive Disease: Yes, No (**Table 23**)

7.5.2 Pre-excision Exam

- Sigmoidoscopy/colonoscopy: normal, abnormal but non-malignant, abnormal and malignant (**Table 24**)
- Other radiology investigations: normal, abnormal but non-malignant, abnormal and malignant (**Table 24**)

7.5.3 Pre-excision Extent of Disease

- Number of patients with disease assessment, number of patients with disease progression, site of diseases, number of disease sites, largest measure (**Table 25**)
 - Number of patients with new lesions, site of new lesions, number of new lesions (**Table 25**)

7.5.4 Plan of Surgical Treatment

Based on the results of pre-excision assessments, a plan of surgical treatment is developed by the investigator. The following information will be summarized (**Table 26**):

- Number of patients with each choice of surgical treatment

7.5.5 Surgical Treatment

The following information on the surgeries performed will be summarized:

- Number of patients who received tumour excision (**Table 27**)
 - Procedure performed: TEMS, TAMIS, TME, other (**Table 27**)
 - Time in operating room: median, minimum, maximum (**Table 27**)
 - Resection margins: R0, R1, R2 (**Table 27**)
 - Mesorectal excision: Total/complete, incomplete, unknown (**Table 27**)
 - Subsequent surgery recommended: Not applicable, Yes but declined by patient, No because complete tumour resection and ypT0 or ypT1good, No other (**Table 27**)
- Number of patients with definitive decision not to have tumour (**Table 27**)
 - Reasons for definitive decision not to have tumour excision (**Table 27**)

7.5.6 Pathology Results after surgical treatment

- Site of the tumor: rectum, nodes, other (**Table 28**)
- Longest dimension of Invasive Carcinoma: median, minimum, maximum values (**Table 28**)
- Lymphatic invasion: Yes, No (**Table 28**)
- Vascular invasion: Yes, No (**Table 28**)
- Histology: adeno-carcinoma, etc. (**Table 28**)
- Histologic grade: well differentiated, moderately differentiation, not stated in report (**Table 28**)
- Deepest layer of invasion: Mucosa, Lamina Propria, Muscularis mucosa, Submucosa, Muscularis propria, Serosa, Perirectal tissue, Subserosa, Not Stated in Report (**Table 28**)
- Depth of invasion into subserosa: median, min-max (**Table 28**)
- Deep margin: positive for invasive carcinoma, negative, not stated in report, not applicable; median, minimum, maximum values (**Table 28**)
- Mucosal margin: positive for invasive carcinoma, negative, not stated in report, not applicable; median, minimum, maximum values (**Table 28**)
- Pathologic T stage: T0, T1, T2, T3, unknown (**Table 28**)
- Number of nodes examined: median, minimum, maximum values (**Table 28**)
- Number of nodes with tumour: median, minimum, maximum values (**Table 28**)
- Tumour deposits: yes, no (**Table 28**)

7.6 Radiation Treatments

Pelvic radiation is recommended for patients when the excisional specimen demonstrates ypT3+ or N+ disease and requires radical TME surgery. The following information will be summarized for patients who received any pelvic radiation therapy prior to TME surgery:

- Site of Radiotherapy: Rectum, Sigmoid colon, Anus (**Table 29**)
- Duration of Radiotherapy (days): median, minimum, maximum (**Table 29**)
- Total dose of radiation: median, minimum, maximum (**Table 29**)

7.7 Efficacy

7.7.1 Organ Preservation Rate

After completion of neoadjuvant chemotherapy, the protocol requires that patients with lesions that on pre-excision (post-chemotherapy) MRI and/or endoscopy showing evidence of progression or no response to chemotherapy to be treated with immediately

the radical TME surgery. Other patients will be treated with local excision TEMS or TAMIS. Patients with ypstage T0/T1goodN0 tumours based on local pathology ypstaging review after TEMS or TAMIS are treated with surveillance while patients with tumours with ypT2, N+ or ypT1 tumours with poor prognostic features are treated with radical TME surgery within 6-8 weeks after local excision. The numbers of enrolled patients who were treated with respectively neoadjuvant chemotherapy, TME and TEMS or TAMIS immediately after completion of neoadjuvant chemotherapy, and TME or surveillance after TEMS or TAMIS will be summarized (**Table 30**).

Organ preservation rate, the primary endpoint of this study, is defined as the proportion of patients with tumour downstaging to ypT0/T1good N0 who avoid radical surgery (TME) among all patients treated with FOLFOX or CAPOX and TEMS or TAMIS. The 95% confidence interval for the organ preservation rate will be calculated (**Table 30**).

Organ preservation rate will additionally be calculated among all patients that have received neoadjuvant chemotherapy.

7.7.2 3 Year Loco-Regional Relapse Rate

Locoregional relapse is defined as reappearance of a tumour within the rectum or pelvis. The number of patients with each site (rectum, pelvis, pelvic lymph nodes, and others) of locoregional relapse will be summarized (**Table 31**).

Locoregional relapse free survival is calculated as time from complete tumour surgical excision date (with pathology results negative for malignant disease within 1 mm of surgical margins) to the first date of definitive evidence (clinical, radiological or pathological) of locoregional relapses. Patients with distant relapse only, died, loss to follow up, or alive at clinical cut-off will be censored at respectively last date of distant relapses, date of death, date of lost to follow-up, and last disease assessment date calculated as the last of dates of attendance/last contact on Follow-up Report.

Kaplan-Meier method (**Figure 2**) will be used to estimate the 3 year loco-regional relapse rate and associated 95% confidence interval first among all patients treated with FOLFOX or CAPOX and TEMS or TAMIS (**Table 31**) and additionally among all patients that have received neoadjuvant chemotherapy.

7.7.3 3 Year Distant Relapse Rate

Distant relapse is defined as appearance of rectal cancer disease at sites remote from the rectum. The number of patients with each site of distant relapse (Lung, Liver, Brain, Distant lymph nodes, Bone, Skin, Ascites, Pleural effusion, Adrenal glands, Other) will be summarized (**Table 31**).

Distant relapse free survival is calculated as time from complete tumour surgical excision date (with pathology results negative for malignant disease within 1 mm of surgical margins) to the first date of definitive evidence (clinical, radiological or pathological) of distant relapses. Patients died, loss to follow up, or alive at clinical cut-off will be censored at respectively date of death, date of lost to follow-up, and last disease assessment date calculated as the last of dates of attendance/last contact on CRD Follow-up Report.

Kaplan-Meier method (**Figure 3**) will be used to estimate the 3 year distant relapse rate and associated 95% confidence interval first among all patients treated with FOLFOX

or CAPOX and TEMS or TAMIS (**Table 31**) and additionally among all patients that have received neoadjuvant chemotherapy.

7.7.4 3 year Disease Free Survival

Disease-Free Survival (DFS) is defined as the interval from complete tumour surgical excision date (with pathology results negative for malignant disease within 1 mm of surgical margins) to date of first occurrence of the events in the below.

- Locoregional relapse reported in CRF Relapse Report
- Distant disease reported in CRF Relapse Report
- Non-protocol radiotherapy, chemotherapy, or biologic therapy without documentation of the site of failure and reported in CRF Chemotherapy Report, Pre-Excision Report, and Surgery Report
- Death due to any other reason reported in CRF Death Report

Patients who are alive without locoregional or distant relapse or receiving non-protocol radiotherapy, chemotherapy, or biologic therapy without documentation of the site of failure at the analysis data cutoff date will be censored at their last disease assessment date calculated as the last of dates of attendance/last contact on Follow-up Report.

A frequency table will be provided describing DFS events and censorings as follows:

- Number of patients who had a DFS event (Relapse (locoregional, distant), non-protocol therapy, death (due to any other reason) (**Table 31**)
- Number of patients censored with reasons of censoring (alive at the clinical cut-off, lost to follow-up) (**Table 31**)

Kaplan-Meier method (**Figure 4**) will be used to estimate the 3 year DFS rate and associated 95% confidence interval first among all patients treated with FOLFOX or CAPOX and TEMS or TAMIS (**Table 31**) and additionally among all patients that have received neoadjuvant chemotherapy.

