13.2 Endpoints and Analysis

The primary endpoint of this study is the protocol specified organ preservation rate, defined as the proportion of patients with tumour downstaging to $ypT0/T1^{good}$ N0 and who avoid radical surgery. The 95% confidence interval for the organ preservation rate will be calculated.

The 3 year locoregional relapse rate, distant relapse rate, and disease free survival will be estimated based on Kaplan-Meier method.

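### The 3-year locoregional and distant relapse rates are read from Kaplan-Meier with deaths censored (and distant relapse too, for the locoregional rate), so they sit at or slightly above the cumulative incidence of relapse

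*SAP*

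**What the plan says.** SAP 7.7.2 measures time from complete excision to definitive evidence of locoregional relapse. Its censoring rule is: "Patients with distant relapse only, died, loss to follow up, or alive at clinical cut-off will be censored". The four groups are "censored at respectively last date of distant relapses, date of death, date of lost to follow-up, and last disease assessment date". Kaplan-Meier "will be used to estimate the 3 year loco-regional relapse rate and associated 95% confidence interval".

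SAP 7.7.3 does the same for distant relapse: "Patients died, loss to follow up, or alive at clinical cut-off will be censored at respectively date of death", and Kaplan-Meier "will be used to estimate the 3 year distant relapse rate and associated 95% confidence interval". Locoregional relapse is not listed there as a reason for censoring.

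Protocol 13.2 agrees on the method: "The 3 year locoregional relapse rate, distant relapse rate, and disease free survival will be estimated based on Kaplan-Meier method".

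Neither document mentions competing risks, cumulative incidence or a sensitivity analysis for these endpoints. The SAP names the two time variables, and the curves in Figures 2 and 3, as forms of relapse-free survival, although death is not an event in either. Death is an event only in DFS (SAP 7.7.4). SAP Table 31 reports LRR and DRR as 3-year percentages with 95% CIs.

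**The concern.** A patient who dies without relapse cannot relapse later. Censoring at death makes Kaplan-Meier treat that patient as if still exposed to the survivors' relapse risk. One minus Kaplan-Meier then describes relapse in a hypothetical setting without deaths, whereas a reader of Table 31 will probably take the figure as the share of patients who relapse within 3 years.

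LRR has a second difficulty. Distant relapse does not prevent local relapse, and the two are unlikely to be independent, so censoring at distant relapse is informative. Read literally, the rule removes early only those patients with distant relapse who never have a recorded local relapse, and keeps patients with both as events. That also pushes the estimate up. DRR has no matching rule for prior locoregional relapse, and no reason is given for the difference.

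At stake is what two secondary descriptive endpoints mean. The trial's decision is not at stake.

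**Working it through.** **Reference figure.** The documents give no expected value, precision or sample size for LRR or DRR, so there is no plan figure to reproduce.

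**Inputs**
- 3-year 1−KM values used for illustration come from Protocol 2.0: 5% (modern adjuvant therapy), 6–14% (T1, local excision) and 18% (T2, local excision plus chemoradiation).
- 3-year competing-event probability C: **an assumption, 2% to 25%**, because the documents give none.
- Number of patients: 50 planned evaluable (Protocol 13.3); 58 accrued (SAP 2.2).

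**Direction, without a model.** Take 50 patients, 5 locoregional relapses and no other censoring. The proportion relapsing is 5/50 = 10.0%.
- With 0 / 2 / 5 / 10 competing events spread over 3 years, 1−KM is 10.0 / 10.2 / 10.5 / 11.2%.
- If all 10 competing events come first, 40 patients remain at risk and 1−KM = 5/40 = 12.5%.
- If all 10 come after the relapses, 1−KM = 10.0%.

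So 1−KM is at or above the cumulative incidence, and equals it only when no competing event precedes a relapse.

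**Size, with constant hazards.** Let F be the 3-year 1−KM, λ = −ln(1−F)/3 and μ = −ln(1−C)/3. The cumulative incidence is

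CIF = λ/(λ+μ) × [1 − (1−F)(1−C)].

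Example with F = 10% and C = 20%: λ/(λ+μ) = 0.1054/(0.1054 + 0.2231) = 0.3207, and 1 − 0.90 × 0.80 = 0.28. CIF = 0.3207 × 0.28 = 8.98%, a gap of 1.02 points.

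CIF, with the overstatement in points in brackets:

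| 1−KM | C = 2% | C = 10% | C = 25% |
|---|---|---|---|
| 5% | 4.95% (0.05) | 4.75% (0.25) | 4.35% (0.65) |
| 10% | 9.90% (0.10) | 9.50% (0.50) | 8.71% (1.29) |
| 14% | 13.86% (0.14) | 13.31% (0.69) | 12.21% (1.79) |
| 18% | 17.83% (0.17) | 17.11% (0.89) | 15.72% (2.28) |

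The overall range is about 0.05 to 2.3 points, or roughly 1% to 15% in relative terms.

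**Where in the range.** The T1N0 part of Protocol 2.0 cites a 10-year DFS of 75% after local excision alone. At constant hazard, h = −ln(0.75)/10 = 0.02877 per year, so 1 − exp(−3h) = 8.3% have any event by 3 years. Suppose, as an assumption, that half are local relapses and half competing events. Then 1−KM = 1 − exp(−1.5h) = 4.22%, CIF = 8.27%/2 = 4.13%, and the gap is 0.09 points. T2 and T3 patients would be expected to do worse, so this is not an upper limit.

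**DRR.** Only death without distant relapse competes. For C of 2% to 5% (assumed), the gap over the same 1−KM values is 0.05 to 0.44 points.

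**Against sampling error.** The 95% half-width 1.96 × √[p(1−p)/50] is 6.0 points at 5%, 8.3 at 10%, 9.6 at 14% and 10.6 at 18%.

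**The case against.** The best case for the plan is that the effect is small and the plan is consistent. Protocol and SAP name the same estimator. The objectives are only to describe these rates. Table 31 shows the counts of locoregional relapse, distant disease and other deaths next to them, so a reader can see how much competing mortality there was. Eligibility (Protocol 4.1 and 4.2) selects N0, M0, ECOG 0–1 patients fit for radical surgery, without active cardiovascular disease or recent other cancer. A 3-year competing-event probability of 20–25% is hard to credit here, least of all for death alone. All of this stands, and it pulls the likely size toward the low end.

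The censoring of distant relapse in LRR also has some logic. Protocol 8.7.1 requires a local work-up when distant disease is found, so local status should be known at about that date. After a first relapse, the Section 5.0 footnotes accept phone contact every 6 months. Later local relapses may therefore be missed, which would pull the estimate down and partly offset the bias.

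Some stronger readings are tempting but unsupported:
- A reader might infer that the plan defines LRR and DRR as patient proportions, or will set them against published rates. It does neither: it uses proportion language for organ preservation, and plans no threshold, test or comparison for LRR or DRR. One background figure, the 11% in the T3N0 part of Protocol 2.0, is itself actuarial, so cumulative incidence would not automatically be more comparable.
- A reader might infer that distant relapse should simply be declared a competing event for LRR. That changes the estimand to locoregional relapse as first failure. Applied to LRR alone, it also keeps the asymmetry with DRR.

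What the objection does not remove is the estimator itself: nothing elsewhere in the documents corrects it.

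**Conclusion.** The point holds as a modest one about estimand and labelling. As written, the 3-year LRR and DRR are at or above the cumulative incidence from the same recorded events. The excess is about 0.05 to 2.3 points under constant hazards and an assumed 2–25% competing-event probability. It is probably near the low end here, and smaller for DRR than for LRR.

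The documents do not support presenting 2.3 points as the expected bias. That figure needs 18% local relapse together with 25% competing events, so only 0.82 × 0.75 = 61.5% would be event-free at 3 years. The excess lies within the confidence interval throughout. The primary endpoint, the two-stage rule and DFS are unaffected. The change is still worth making, because a wide interval does not justify estimating a different quantity from the one readers will understand.

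**What to change.** In SAP 7.7.2 and 7.7.3:

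1. Report 3-year LRR and DRR as Aalen-Johansen cumulative incidence with 95% CI, with death without the relevant relapse as the competing event.
2. For LRR, stop treating distant relapse as independent censoring, and choose one of two definitions in advance. Either keep patients at risk for local relapse after distant relapse, using whatever local status is recorded and stating that assessment is then less regular. Or report locoregional relapse as first failure, with distant relapse competing, label it so, and apply the parallel rule to DRR.
3. Keep 1−KM as a sensitivity analysis, since Protocol 13.2 names it, and record the departure.
4. Relabel the time variables and Figures 2 and 3 as time to relapse or cumulative incidence, because death is not an event in them.
5. Leave Kaplan-Meier for DFS.

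The cost is SAP wording, a standard SAS option, slightly more analysis work and a small departure from the method named in the protocol. Relapse dates and sites and death dates are already collected (Protocol 8.7.1 and Appendix III), so no new data are needed.

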8.0 CRITERIA FOR MEASUREMENT OF STUDY ENDPOINTS

8.1 Definitions

8.1.1 *Evaluable for Organ Preservation Rate*

All patients treated with FOLFOX or CAPOX and TEMS or TAMIS will be included in the organ preservation rate analysis as primary endpoint of this study.

Organ preservation rate will additionally be calculated for all patients that have received protocol chemotherapy.

8.1.2 *Evaluable for Rectal Cancer Control*

All patients treated with FOLFOX or CAPOX and TEMS or TAMIS will be evaluated for locoregional and distant relapse rate.

Rectal cancer control will additionally be calculated for all patients that have received protocol chemotherapy.

8.1.3 *Evaluable for Disease Free Survival*

All patients treated with FOLFOX or CAPOX and TEMS or TAMIS will be evaluable for assessment of disease free survival.

Disease Free Survival will additionally be calculated for all patients that have received protocol chemotherapy.

8.1.4 *Evaluable for Post-Operative Complications*

All patients treated with FOLFOX or CAPOX and tumour excision/surgery will be evaluable for post-operative complications.

8.1.5 *Evaluable For Adverse Events*

All patients who have received at least one dose of protocol chemotherapy will be included in the safety analysis.

8.1.6 *Evaluable for Quality of Life Assessment*

All patients who have completed a quality of life questionnaire are evaluable for quality of life.

8.2 *Evidence of Disease Progression/No Response After Chemotherapy*

8.2.1 *Progression*

The diagnosis of progressive disease will be made by treating surgeon after review of the pre-excision (post-chemotherapy) MRI and endoscopy.

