8.7 Disease Free Survival

Disease-Free Survival (DFS) is defined as the interval from complete tumour surgical excision date (with pathology results negative for malignant disease within 1 mm of surgical margins) to date of first occurrence of the events in the table below.

Patients not meeting the criteria for failure by the analysis data cutoff date will be censored at their last disease assessment date.

First Event	Disease Free Survival
None	Censored
Locoregional relapse	Failure
Distant disease	Failure
Non-protocol radiotherapy, chemotherapy or biologic therapy without documentation of the site of failure	Failure
Death due to any other reason	Failure

8.7.1 Capture of Failures and Work-up at Detection of First Failure:

Only the first event experienced will determine a patient's failure status for DFS analysis. However, in order to fully capture the patterns of failure in this study population, a detailed work-up at the time of the first failure is required, and sites of failures should be documented in the CRF.

For instance, if a patient first develops locoregional relapse, then a work-up for distant metastasis will be performed at the same time. If the distant metastatic work-up reveals the presence of distant metastasis, then all sites of failure will be documented, even though the time of the first detected failure event will be used to determine the disease free survival. Similarly, if a patient is first found to have distant metastasis, then a work-up for locoregional relapse should be performed at the same time. If the locoregional work-up does not reveal relapse at the same time, then this patient is considered to only have distant disease failure.

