4.3 Safety

The safety endpoints are post-operative complication rate, serious and non-serious adverse events (clinical and laboratory), laboratory parameters, dosing data (including dose interruptions, total delivered dose and dose modifications) and reasons off treatment.

5. Sample Size and Power

The expected organ preservation rate is 50-68% among patients with clinical T1-3N0 rectal tumours treated with chemoradiation and minimally invasive surgery. Based on these historic phase II data, the experimental treatment would be considered of no interest if the protocol specified organ preservation rate is 50% or lower (H_0) and as promising if its avoidance rate is 65% or higher (H_1).

An optimal two-stage minimax design would be used to test the above hypotheses, which would accrual 22 evaluable patients in the first stage. The trial would be stopped at the end of the first stage if the number of patients who avoided radical surgery is 10 or less. Otherwise the trial would proceed to the second stage to accrue 28 additional evaluable patients. The experimental procedure would be considered as promising if, out of the total patients accrued, 30 or more patients avoided radical surgery. The exact type I error rate and power of this design are respectively 0.1 and 0.8. Allowing for a 15% inevaluable rate, the total sample size would be 58 patients.

6. Data Set Descriptions

Five types of analysis samples will be used:

1. All Accrued Patients:

All patients accrued in the study.

2. All Chemotherapy Treated Patients:

All patients who have received at least one dose of FOLFOX or CAPOX.

3. All Chemotherapy & Excision Treated Patients

All patients who have received at least one dose of FOLFOX or CAPOX and TEMS or TAMIS.

4. All Chemotherapy & Excision/Surgery Treated Patients

All patients who have received at least one dose of FOLFOX or CAPOX and excision (TEMS or TAMIS) or surgery (TME).

5. All Quality of Life Evaluable Patients

All patients who have completed at least one quality of life questionnaire.

7. Statistical Analysis

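### Relapse and DFS in all chemotherapy-treated patients are timed from complete excision, so patients never completely excised have no start time and the Kaplan-Meier estimates are conditional on complete excision

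*SAP*

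**What the plan says.** The three endpoints share one time origin. SAP 7.7.2 states that "Locoregional relapse free survival is calculated as time from complete tumour surgical excision date", SAP 7.7.3 that "Distant relapse free survival is calculated as time from complete tumour surgical excision date", and SAP 7.7.4 that "Disease-Free Survival (DFS) is defined as the interval from complete tumour surgical excision date". Each adds that pathology must show clear margins at 1 mm. Protocol 8.7 agrees: DFS "is defined as the interval from complete tumour surgical excision date".

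Each endpoint is estimated by Kaplan-Meier first in patients who had chemotherapy and TEMS or TAMIS, then "additionally among all patients that have received neoadjuvant chemotherapy". Protocol 8.1.3 makes the same commitment: "Disease Free Survival will additionally be calculated for all patients that have received protocol chemotherapy". A note after SAP Figure 4 repeats Table 31 and Figures 2 to 4 for that set. SAP section 6 defines the set as "All patients who have received at least one dose of FOLFOX or CAPOX"; excision is not a condition of entry.

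The plan expects some patients not to reach complete excision. SAP 7.5.5 tabulates "Reasons for definitive decision not to have tumour excision", and Table 27 lists progression, intercurrent illness, refusal and death among them. Table 27 also has rows for R1 and R2 margins and for further surgery that the patient declined. Table 41 counts deaths before surgery.

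**The concern.** The stated origin does not fit the stated population. Without a complete-excision date no Kaplan-Meier time can be computed, and neither document gives a substitute origin, event rule or censoring rule. The analyst must either leave these patients out, so that the result is conditional on successful surgery while labelled as all treated, or choose a rule once the data are known.

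This set supplies the only planned relapse and DFS estimates not restricted to patients who went to TEMS or TAMIS. A reader will take them as the outcome of starting the chemotherapy strategy. Some of the patients left without a start time, notably those who die before surgery or progress without resection, are clear failures of that strategy.

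**Working it through.** **Who has a start date.** The texts can be set side by side.

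- Progression or no response, then TME with clear margins: Protocol 7.3 and SAP 7.7.1 send these patients to TME. The origin is not limited to TEMS or TAMIS, so they have a date and are not affected.
- Positive margin at TEMS or TAMIS, then a clear-margin TME: date exists, not affected.
- Progression never resected, death before surgery, or refusal of all surgery: no date.
- Margin under 1 mm with no further clearing surgery: no date. This group also sits in the TEMS/TAMIS set, so the main analysis has a smaller version of the same gap.

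**Whether other rules close the gap.** They do not.

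- Death from another cause is a listed DFS event (SAP 7.7.4), but before surgery it precedes an origin that never occurs.
- The non-protocol-therapy event is read from the Chemotherapy, Pre-Excision and Surgery Reports, so it too can precede time zero.
- The censoring date comes from the Follow-up Report, whereas Protocol Appendix III puts patients with no protocol excision on the Short Follow-up form.
- The listed censoring reasons are alive at cut-off and lost to follow-up; neither describes a patient who was never excised.

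**Size.** The documents give no expected DFS or relapse rate and no count of never-excised patients, so there is no figure of the plan's own to reproduce. What follows is an illustration.

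Inputs:
- N = 58, the number accrued (SAP 2.2) and so the upper limit for this set.
- k = number never completely excised; assumed 1 to 6.
- S = 3-year DFS in completely excised patients; assumed 85%, range 80% to 95%.
- f = proportion of the k patients who are event-free at 3 years; bounded by 0 and 1.
- The shift in time origin is ignored.

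DFS in all treated = [S(N − k) + f k] / N, so the overstatement = (k/N)(S − f).

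| k | all k fail (f = 0) | overstatement | all k event-free (f = 1) |
|---|---|---|---|
| 1 | 0.85 × 57/58 = 83.5% | 1.5 points | (0.85 × 57 + 1)/58 = 85.3% |
| 3 | 0.85 × 55/58 = 80.6% | 4.4 points | (0.85 × 55 + 3)/58 = 85.8% |
| 6 | 0.85 × 52/58 = 76.2% | 8.8 points | (0.85 × 52 + 6)/58 = 86.6% |

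For f = 0 and S from 80% to 95%, the overstatement is 1.4 to 1.6 points at k = 1, 4.1 to 4.9 at k = 3 and 8.3 to 9.8 at k = 6. The sign depends only on whether never-excised patients do worse than excised ones (f below S).

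**The case against.** The case against is strong on scope.

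- A reader might infer that everyone who progresses drops out. The documents do not support that: the planned route after progression is TME, and a clear-margin TME supplies the date.
- A reader might infer that the SAP excludes these patients. It says nothing of the kind. It is silent, and their loss follows from an undefined time.
- A reader might infer that a death before surgery cannot be counted at all. Table 31 also asks for a frequency count of DFS events, repeated for this set, and nothing bars such a death from it. Only the Kaplan-Meier estimate has no place for it, so the count and the curve could disagree.
- A reader might infer that relapse is understated. That is not shown. Locoregional relapse means reappearance of tumour, which has no meaning for a tumour never removed, and the calculation above concerns DFS only.
- The affected patients stay visible in Tables 27, 30, 40 and 41.
- Neither document says the additional analysis is meant to remove selection. It may serve mainly to add patients who went straight to TME. The stated objectives concern patients treated with organ preservation, so this is a supporting analysis of descriptive secondary endpoints.

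All of this narrows the point. None of it supplies a time zero for a population that the plan has committed to analyse.

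**Conclusion.** The point holds in limited form. The all-treated Kaplan-Meier estimates are, as written, conditional on complete excision. Three-year DFS in this set is likely overstated, because death before surgery and unresected progression are among the ways to lack a start date. That direction is a judgement, not a certainty: patients who refuse surgery need not fail, and if all never-excised patients were event-free the bias would be small and reversed. The size, about 1.5 points for one patient and about 9 for six, rests on assumed counts, an assumed 85% DFS and failure of every never-excised patient. The organ preservation endpoint and its decision rule are not affected.

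**What to change.** - In the all-chemotherapy-treated set, start DFS at enrolment or first dose. Count death from any cause (including before surgery), progression never resected, and relapse as events.
- Follow never-excised patients without an event to their last contact, taking dates from the Short Follow-up and Death Reports as well as the Follow-up Report.
- Keep the excision-origin estimates of locoregional relapse, distant relapse and DFS, labelled as conditional on complete excision.
- For each analysis set, including TEMS/TAMIS, report how many patients lack a complete-excision date and why.
- Treat refusal of surgery or a positive margin alone as a DFS event in a sensitivity analysis at most; making either an event in the main definition would change the endpoint.

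The cost is SAP text and one derived date. The dates needed are already used in SAP 7.2.1 (accrual) and 7.4.1 (first treatment). The supportive figure will probably be less favourable. It will also not be directly comparable with the excision-origin figure, because the clock starts earlier. On the planned schedule, excision falls 12 to 15 weeks after first dose: for FOLFOX, 5 × 14 days = 10 weeks to cycle 6, plus 2 to 5 weeks; for CAPOX, 3 × 21 days = 9 weeks to cycle 4, plus 3 to 6 weeks. The table note should say so.
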